8.2.2 Biospecimen Evaluations

Blood will be collected under this protocol by the following methods:

- Venipuncture will be performed with single-use needles. Venous blood samples will be used as follows:
 - Safety evaluations described in section [8.3](#).
 - Shipment to the research laboratory in Bamako and NIAID for evaluation (including assays described in section [8.2.3](#)) and storage.
 - Blood smear and dried blood spot for PfRT-PCR if unable to obtain ample sample from finger prick
- Fingerprick will be performed using single-use disposable lancets. Fingerprick blood samples will be used as follows:
 - Blood smear and dried blood spot for Pf RT-PCR.

The amount of blood drawn for research purposes will be within the limits allowed for adult research subjects by the NIH Clinical Center: no more than 10.5 mL/kg or 550 mL (whichever is smaller) over an 8-week period.

The collection schedule, volumes, and test tubes are presented in section [1.3](#).

Abbreviated Title: Anti-malaria MAb in Mali

Version Date: October 13, 2022

8.2.3 Correlative Studies for Research/Pharmacokinetic Studies

The following evaluations will be performed according to the schedule presented in section [1.3](#).

Blood smear: Thick blood smears will be prepared and analyzed by the standard WHO method (section [2.2.3.3](#)) to identify Pf infection for the primary endpoint. This evaluation will be performed centrally in the laboratory in Bamako.

Pf RT-PCR: RT-PCR will be performed to identify Pf infection as a secondary endpoint. This evaluation will be performed at the University of Washington on coded dried blood spots.

PK studies: Blood CIS43LS concentrations will be measured by Meso Scale Discovery LLC-based automation platform. The concentration at the visit prior to the first Pf infection will be used to assess CIS43LS-mediated protection. This evaluation will be performed at the NIAID.

ADA detection: Assays for detection of ADA will be performed at specified timepoints (section [1.3](#)) following product administration and compared to baseline status. This evaluation will be performed at the NIAID.

Parasite genotyping: For subjects who become infected during the study, coded blood samples collected around the time of the first infection will be used to perform a genotypic sieve analysis to analyze sequences of breakthrough parasites (section [9.4.11](#)). This evaluation will be performed by [name] at the Harvard School of Public Health.

8.2.4 Samples for Genetic/Genomic Analysis

8.2.4.1 Description of the scope of genetic/genomic analysis

Genetic testing performed in this protocol will be limited to analyzing the genetic material of infection-inducing parasites in blood samples. No human genetic analyses will be performed.

8.2.4.2 Description of how privacy and confidentiality of medical information/biological specimens will be maximized

Privacy and confidentiality of medical information and biological samples is described in section [10.3](#).

8.2.4.3 Management of Results

As no human genetic analyses will be performed in this protocol, no genetic results will be returned to subjects.

8.2.4.4 Genetic counseling

Not applicable.

8.3 SAFETY AND OTHER ASSESSMENTS

The following study procedures and evaluations will be done according to the schedule in section [1.3](#) to monitor safety and support the understanding of the study intervention's safety. The assessment and collection of safety events such as AEs are described in section [8.4.2](#).

Abbreviated Title: Anti-malaria MAb in Mali

Version Date: October 13, 2022

Physical Examination: As described in section 8.2.1, physical examination will also be performed for assessment of safety.

Vital Signs: Vital signs (temperature, blood pressure, and heart rate) will be collected at visits, including before and after study agent infusion, as described in section 8.2.1.

Safety Blood Laboratory Evaluations: The following safety laboratory evaluations will be performed at a frequency presented in section 1.3:

- CBC with differential.
- ALT, Cr.

Pregnancy Testing: Women will have a serum pregnancy test at screening and urine tests at enrollment, day 0 (confirmed negative prior to administration of the study agent), and monthly through the final study visit.

Pregnancy Prevention Counseling: Female subjects will be counseled on the importance of not becoming pregnant during study participation and on acceptable methods of contraception.

8.4 SAFETY DEFINITIONS, MANAGEMENT, AND SPONSOR REPORTING

8.4.1 Definitions

Adverse Event: An AE is any untoward or unfavorable medical occurrence in a human subject, including any abnormal sign (e.g., abnormal physical exam or laboratory finding), symptom, or disease, temporally associated with the subject's participation in the research, whether or not considered related to the research.

Adverse Reaction: An AR means any AE caused (see "Causality" below) by a study agent. ARs are a subset of all suspected adverse reactions (SARs; defined below) where there is reason to conclude that the study agent caused the event.

Suspected Adverse Reaction: SAR means any AE for which there is a reasonable possibility that the study agent caused the AE.

Per US FDA guidance:

For the purposes of IND safety reporting, "reasonable possibility" means there is evidence to suggest a causal (see "Causality" below) relationship between the study agent and the AE. A SAR implies a lesser degree of certainty about causality than an AR, which means any AE caused by a study agent.

SARs are the subset of all AEs for which there is a reasonable possibility that the study agent caused (see "Causality" below) the event. Inherent in this definition, and in the requirement to report SARs, is the need for the sponsor to evaluate the available evidence and make a judgment about the likelihood that the study agent actually caused the AE.

The sponsor is responsible for making the causality judgment.

Serious Adverse Event: An SAE:

- is an AE that results in death.

Abbreviated Title: Anti-malaria MAb in Mali

Version Date: October 13, 2022

- is an AE that is life-threatening event (places the subject at immediate risk of death from the event as it occurred).
- is an AE that requires inpatient hospitalization or prolongs an existing hospitalization.

NOTE:

- Hospitalization is considered required if outpatient treatment would generally be considered inappropriate.
- Same-day surgical procedures that are required to address an AE are considered hospitalizations, even if they do not involve an overnight admission.
- Hospitalization due to a condition that has not worsened and that pre-dates study participation (e.g., elective correction of an unchanged baseline skin lesion), or due to social circumstance (e.g., prolonged stay to arrange aftercare), or that is planned/required “per protocol” AND that proceeds without prolongation or complication, is NOT considered an SAE by this criterion.
- is, or results in, a persistent or significant incapacity or substantial disruption of the ability to conduct normal life functions.
- is a congenital anomaly/birth defect/miscarriage/stillbirth.

NOTE: This definition is more inclusive than some commonly published definitions. It includes an affected conceptus/neonate whose:

- biological mother was exposed to a study agent at any point from conception through the end of the pregnancy, AND/OR, if breastfeeding, the 30-day neonatal period; or
- biological father was exposed to a study agent at any point during the 90 days prior to conception.

This is separate from, and in addition to, general reporting of pregnancy in a study participant or female partner of a male participant (see section [8.4.2.3.4](#) below).

- is a medically important event.

NOTE: Medical and scientific judgment should be exercised. Events that significantly jeopardize the subject and/or require intervention to prevent one of the SAE outcomes listed above are generally considered medically important, and are thus SAEs.

Unexpected Adverse Event: An AE is unexpected if it is not listed in the investigator’s brochure or package insert (for marketed products) at the frequency, AND specificity, AND severity that has been observed.

NOTE:

- Such events should also be evaluated for possible reporting as unanticipated problems (UPs) (see section [8.4.2.3.3](#) below).
- Unexpected, as used in this definition, also refers to AEs or SARs that are mentioned in the investigator’s brochure as occurring with a class of drugs/biologics, or as anticipated from the pharmacological properties of the study agent but are not specifically mentioned as occurring with the particular study agent under investigation.

Abbreviated Title: Anti-malaria MAb in Mali

Version Date: October 13, 2022

Serious and Unexpected Suspected Adverse Reaction (SUSAR): A SUSAR is an SAR (defined above) that is both serious and unexpected.

Unanticipated Problem: A UP is any incident, experience, or outcome that meets all the following criteria:

1. Unexpected (in terms of nature, severity, or frequency) given
 - a. the research procedures that are described in the protocol-related documents, such as the EC-approved research protocol and informed consent document; and
 - b. the characteristics of the subject population being studied; and
2. Related or possibly related to participation in the research (possibly related means there is a reasonable possibility that the incident, experience, or outcome may have been caused by the procedures involved in the research), and
3. Suggests the research places subjects or others (which may include research staff, family members or other individuals not directly participating in the research) at a greater risk of harm (including physical, psychological, economic, or social harm) related to the research than was previously known or expected.

NOTE:

- Per the sponsor, an SAE always meets this “greater risk” criterion.
- An incident, experience, or outcome that meets the definition of a UP generally will warrant consideration of changes to the protocol or informed consent form, or to study procedures (e.g., the manual of procedures for the study), in order to protect the safety, welfare, or rights of participants or others. Some UPs may warrant a corrective and preventive action plan at the discretion of the sponsor or other oversight entities.

Unanticipated Problem that is not an Adverse Event (UPnonAE): A UPnonAE belongs to a subset of UPs that:

- meets the definition of a UP, AND
- does NOT fit the definition of an AE or an SAE.

NOTE: Examples of UPnonAEs include, but are not limited to:

- a breach of confidentiality
- prolonged shedding of a vaccine virus beyond the anticipated timeline
- unexpectedly large number of pregnancies on a study
- subject departure from an isolation unit prior to meeting all discharge criteria
- accidental destruction of study records
- unaccounted-for study agent
- overdosage, underdosage, or other significant error in administration or use of study agent or intervention, even if there is no AE/SAE
- development of an actual or possible concern for study agent purity, sterility, potency, dosage, etc.

NOTE: A decision to temporarily quarantine, or to permanently not use all or part of study agent supply due to an unexpected finding or event (e.g., particulate, cloudiness, temperature excursion), even if there is no known or

Abbreviated Title: Anti-malaria MAb in Mali

Version Date: October 13, 2022

proven issue (i.e., out of an “abundance of caution”), is considered a UPnonAE.

Protocol Deviation: Any change, divergence, or departure from the EC-approved research protocol.

1. **Major deviations:** Deviations from the EC-approved protocol that have, or may have the potential to, negatively impact the rights, welfare, or safety of the subject, or to substantially negatively impact the scientific integrity or validity of the study.
2. **Minor deviations:** Deviations that do not have the potential to negatively impact the rights, safety, or welfare of subjects or others, or the scientific integrity or validity of the study.

Noncompliance: Failure of investigator(s) to follow the applicable laws, regulations, or institutional policies governing the protection of human subjects in research, or the requirements or determinations of the EC, whether intentional or not.

1. **Serious noncompliance:** Noncompliance, whether intentional or not, that results in harm or otherwise materially compromises the rights, welfare and/or safety of the subject. Noncompliance that materially affects the scientific integrity or validity of the research may be considered serious non-compliance, even if it does not result in direct harm to research subjects.
2. **Continuing noncompliance:** A pattern of recurring noncompliance that either has resulted, or, if continued, may result in harm to subjects or otherwise materially compromise the rights, welfare and/or safety of subjects, affect the scientific integrity of the study or validity of the results. The pattern may comprise repetition of the same non-compliant action(s), or different noncompliant events. Such non-compliance may be unintentional (e.g., due to lack of understanding, knowledge, or commitment), or intentional (e.g., due to deliberate choice to ignore or compromise the requirements of any applicable regulation, organizational policy, or determination of the EC).

8.4.2 Documenting, Assessing, Recording, and Reporting Events

ALL AEs, including those that may appear to have a non-study cause (see “Causality” below), will be documented (e.g., on the clinical chart/progress notes/clinical laboratory record), recorded (e.g., in the study-specified CRF/research database), and reported (e.g., cumulatively from the research database, or according to protocol-specified expedited reporting mechanism) to the sponsor from the time informed consent is obtained through the timeframe specified below. At each contact with the subject, information regarding AEs will be elicited by open-ended questioning and examinations.

AEs and SAEs will generally be recorded, assessed, and reported according to the timeframes outlined in [Table 2](#).

Abbreviated Title: Anti-malaria MAb in Mali

Version Date: October 13, 2022

Table 2. Standard event recording, assessment, and reporting timeframes.

Event type	Record, assess, and report through
Related SAEs	End of subject participation in study, or if study personnel become aware thereafter
Unrelated SAEs	End of subject participation in study
Related non-serious AEs of grade 1 to 3	End of subject participation in study
All other related non-serious AEs	End of subject participation in study
Unrelated non-serious AEs	End of subject participation in study

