³ Enrollment is defined as the time of first artemether-lumefantrine administration. (For women, negative pregnancy test must be confirmed prior to administration/enrollment.) The first dose will be directly observed in the clinic. The subsequent 5 doses given over 3 days will be observed by guides in the subject's home or at the clinic. All artemether-lumefantrine doses will be completed prior to day 0.

⁴ All other study procedures must be completed prior to study agent infusion. Subject will be monitored during and after each infusion, and vital signs will be recorded directly after infusion and hourly during post-infusion monitoring. The first subject in a dose arm will be monitored for at least 4 hours after completion of infusion; all other subjects will be monitored for at least 2 hours after completion of infusion. Prior to discharge, subject will be assessed for local reactogenicity (including pain/tenderness, swelling, redness, bruising, and pruritus at the site of infusion) and systemic reactogenicity (including fever, feeling unusually tired or unwell, muscle aches, headache, chills, nausea, and joint

Abbreviated Title: Anti-malaria MAb in Mali

Version Date: October 13, 2022

Study Day	Screen	Enroll ¹	0	1	3	7	14	21	28	56	84	112	140	168	Illness Visit	ET Visit
Window (days)	-56 to -7	-14±7	-	+1	±1	±2	±3	±3	±3	±7	±7	±7	±7	±7		

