Treatments with these MAbs have been generally well tolerated, with no reported deaths or serious adverse events (SAEs) assessed as related to the study products. Typical for MAbs, the predominant local reactogenicity complaint has been mild pain/tenderness, although reports of mild injection-site pruritus, redness and swelling have occurred at modestly higher frequencies with SC administration. Malaise, muscle pain, and headache have been the most frequently reported solicited complaints noted in the 3 days after product administration, and these have also been mostly transient and mild in severity. Urticaria and infusion reactions including chills, rigors, myalgia, headache, and/or fever have been reported after IV infusions at product doses of 10 to 40 mg/kg; these reactions have been transient, resolved without sequelae within 24 hours of onset, and were treated with over-the-counter analgesics and antipyretics.

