In the dose-escalation study, the first subject in each dose arm to receive a unique dose level will be observed for at least 4 hours following completion of initial product administration. All other subjects will be observed for at least 2 hours following completion of product administration. In the efficacy study, all subjects will be observed for at least 60 minutes following administration. Prior to discharge from the clinic, vital signs will be recorded and subjects will be assessed for local reactogenicity (including pain/tenderness, swelling, redness, bruising, and pruritus at the site of infusion) and systemic reactogenicity (including fever, feeling unusually tired or unwell, muscle aches, headache, chills, nausea, and joint pain). Any subject who is assessed as being unwell or has ongoing reactogenicity symptoms will be asked to remain in the clinic until evaluation and discharge by a study clinician. If necessary, the subject would be referred to the district hospital to evaluate for safety and possible treatment. Clinicians will follow any solicited symptoms that are ongoing until they have resolved.

Abbreviated Title: Anti-malaria MAb in Mali

Version Date: October 13, 2022

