9 STATISTICAL CONSIDERATIONS

9.1 STATISTICAL HYPOTHESIS

The hypotheses are that CIS43LS will be safe and will confer protection against Pf infection. In the dose-escalation study, the primary objective is to evaluate the safety and tolerability. In the efficacy study, the primary objective is to evaluate the safety and efficacy of CIS43LS compared to placebo.

Primary Endpoints:

- Dose escalation: Incidence and severity of local and systemic AEs occurring within 7 days after the administration of CIS43LS
- Efficacy: Pf blood stage infection as detected by microscopic examination of thick blood smear for 24 weeks after administration of CIS43LS or placebo

Abbreviated Title: Anti-malaria MAb in Mali

Version Date: October 13, 2022

Secondary Endpoints:

- Dose escalation: Measurement of CIS43LS in sera of recipients
- Efficacy: Pf blood stage infection as detected by RT-PCR for 24 weeks after administration of CIS43LS or placebo
- Efficacy: Measurement of CIS43LS in sera of recipients

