9.4.5 Safety Analyses

Safety analysis will be primarily MITT where individuals who receive assignment but do not receive any product are excluded. Because of blinding and the brief length of time between assignment and administration, such cases will be very few.

Safety data will be presented by line listing and tables at the individual level to provide details on safety events such as severity, duration, and relationship to study product. The number and percentage of subjects with 1 or more AEs will be summarized by dose arm along with the exact 95% confidence intervals of the AE rate. For subjects experiencing more than 1 AE, the subjects will be counted once under the event of highest severity.

In the efficacy study, comparisons between the dose arms and the control arm will be additionally performed in terms of the proportions of solicited AEs, related AEs, and SAEs.

In the rare case of subjects receiving a regimen different from assignment, a per-protocol analysis will be performed as a secondary analysis, which will include subjects according to the product they actually receive in the study.

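### No symptom list is described after discharge on day 0, so solicited AEs are undefined in 9.4.5 and later mild subjective symptoms are likely to be under-captured

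*Combined protocol and SAP*

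**What the plan says.** **When the list is asked.** Section 6.1.2.4 (Drug Administration) names the local symptoms (pain or tenderness, swelling, redness, bruising, itching) and the systemic ones (fever, tiredness or feeling unwell, muscle aches, headache, chills, nausea, joint pain). It places the assessment on day 0: "Prior to discharge from the clinic, vital signs will be recorded and subjects will be assessed for local reactogenicity". Minimum observation after infusion is 60 minutes in the efficacy study. In dose escalation it is 2 hours, or 4 hours for the first subject in each arm. Footnote 4 of the dose-escalation schedule (1.3.1) agrees: "Prior to discharge, subject will be assessed for local reactogenicity". Footnote 4 of the efficacy schedule (1.3.2) has the same timing.

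**What happens afterwards.** Section 6.1.2.4 adds: "Clinicians will follow any solicited symptoms that are ongoing until they have resolved". That covers symptoms already present at discharge. For every contact, 8.4.2 states that "information regarding AEs will be elicited by open-ended questioning and examinations". Section 8.3 lists physical examination, vital signs, safety laboratory tests, and pregnancy testing and counseling. It mentions no symptom checklist, diary or memory aid.

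**What the analysis uses.** The dose-escalation primary endpoint (9.1) is "Incidence and severity of local and systemic AEs occurring within 7 days after the administration of CIS43LS". In the efficacy study, 9.4.5 compares the dose arms with control "in terms of the proportions of solicited AEs, related AEs, and SAEs". Neither the meaning of solicited nor a time window is given.

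**What the background says.** For related monoclonal antibodies, 2.2.2.1 reports: "Malaise, muscle pain, and headache have been the most frequently reported solicited complaints noted in the 3 days after product administration".

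**The concern.** A solicited AE is normally one obtained by asking about a named symptom. If the list is asked only before discharge, then read literally the comparison in 9.4.5 covers roughly the first hour or so after infusion in the efficacy study. A headache that starts on day 2 is either not solicited, or is counted as solicited although nobody asked about it by name. Two analysts could produce different tables from the same data.

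The second issue is completeness. The protocol's own background places the common complaints over 3 days, most of which follow discharge. It also says that infusion reactions with related products resolved within 24 hours of onset (2.2.2.1). Such a reaction can be over by the day 1 visit, which has a window of +1 day, and an examination cannot detect a headache that has gone. Whether a mild, resolved symptom is recorded then depends on how the open question is put and answered, often through oral translation, since most potential subjects do not read or speak French (10.1.1.2). What is at stake is the tolerability profile: rates of mild and moderate symptoms, and the power to show a difference in them.

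**Working it through.** **Step 1: set the sections side by side.**

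- Named list: before discharge on day 0 (6.1.2.4; footnote 4 of both schedules).
- After discharge: ongoing solicited symptoms are followed (6.1.2.4), and other AEs are sought by open question and examination at each contact (8.4.2).
- AE review visits inside 7 days: days 1, 3 and 7 (1.1; 4.1).
- Analyses that depend on this: AEs within 7 days in dose escalation (9.1), and solicited AEs by arm in the efficacy study (9.4.5).

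No section in the available text links the list to days 1, 3 or 7.

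**Step 2: reproduce the plan's own figures.** Table 3 gives Pr(0) = (1 − p)^n. At p = 0.2 and n = 6, 0.80^6 = 0.262, as printed. At p = 0.1, 0.90^6 = 0.531, as printed.

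Table 5 (n = 110 per arm, two-sided 0.025, placebo rate 5.0%) gives a detectable rate of 18.2% at 80% power. The pooled-variance normal approximation is

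power = Φ{ [√n·(p2 − p1) − z·√(2p̄(1 − p̄))] / √(p1(1 − p1) + p2(1 − p2)) }.

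With p1 = 0.05, p2 = 0.182, p̄ = 0.116 and z = 2.241, this is (1.384 − 1.015)/0.443 = 0.83, so power is 0.798, which matches. Both tables implicitly assume that every event is captured.

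**Step 3: allow for missed events.** The documents give no capture fraction, so the missed fraction m is an assumption shown over a range. The recorded rate is p(1 − m), applied equally to both arms in the power columns.

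| Missed fraction m (assumed) | Recorded rate, true 20% | Pr(no event), n = 6 | Power, true 18.2% vs 5.0%, alpha 0.025 | Same, alpha 0.05 |
|---|---|---|---|---|
| 0 | 20% | 0.80^6 = 0.262 | 80% | 87% |
| 10% | 18% | 0.82^6 = 0.304 | 74% | 83% |
| 25% | 15% | 0.85^6 = 0.377 | 64% | 74% |
| 50% | 10% | 0.90^6 = 0.531 | 44% | 55% |

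Both alpha levels are shown because Table 5 uses 0.025, while the default in 9.4.1 is 0.05 and 9.4.5 sets no other level.

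**Step 4: which row is plausible.** The fraction m applies to all events counted, but only subjective symptoms with onset after discharge are much exposed. If, for illustration, half of the events are of that kind and half of those are missed, the overall loss is 0.5 × 0.5 = 25%. The recorded rate is then 0.20 × 0.75 = 15% and Pr(0) = 0.377. A 50% overall loss would need nearly every event to be exposed, or nearly every exposed event to be missed.

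**The case against.** **That the list is certainly never asked after day 0.** A reader might infer this, but the documents do not settle it. The clinical-procedure rows of the dose-escalation schedule and its footnotes after footnote 4 are not in the available text, and some rows of the efficacy schedule are also missing. The reading rests on the narrative and the efficacy-schedule footnotes. If a missing row does ask the list on days 1 to 7, it would conflict with 8.4.2 and still need reconciling.

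**That later symptoms are recorded only if volunteered.** This goes too far. Section 8.4.2 includes examinations. Later visits also have a targeted history, medication review and targeted physical examination (8.2.1) and vital signs (8.3), and all concomitant medication is recorded (6.5). Fever is measured, and swelling, redness and bruising can be seen. Capture is incomplete for subjective symptoms, not absent.

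**That a 7-day reactogenicity endpoint is compromised.** No such endpoint exists. The dose-escalation endpoint is local and systemic AEs, and seeking those by open question is not a contradiction. The solicited-AE comparison belongs to the efficacy study and is an additional analysis.

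**That the safety gate fails.** Pausing and halting (8.4.5, 8.4.6) turn on related, unexpected SAEs or grade 3 or higher AEs, which subjects are more likely to report. Nothing shows that missed mild symptoms would change a pause, halt or escalation decision.

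**On the background.** The 3-day statement concerns other antibodies, includes day 0, and does not say that onset followed discharge.

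These points narrow the concern. What stands is an undefined term in a planned comparison, and no described means of asking about listed symptoms that begin after discharge.

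**Conclusion.** The point holds in limited form. As far as the available text shows, the symptom list is tied to discharge on day 0, later contacts use open questions and examination, and 9.4.5 compares solicited AEs with no definition or window. Headache, malaise, muscle ache, chills, nausea and joint pain of mild to moderate grade that begin after discharge are likely to be under-captured. Fever, visible local signs, laboratory events and grade 3 or higher events are less affected.

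In the efficacy study, blinding should make the loss similar across arms. The expected effect is therefore lower recorded rates and lower power; the documents give no ground for inferring a reversed or spurious difference between arms. The size cannot be derived from the documents. The 10% to 50% range is an assumption, and its upper end treats half of all events as lost, which probably overstates the effect given the other means of detection. This is a low-cost improvement worth making, not a flaw that invalidates the safety assessment or the primary endpoint.

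**What to change.** - **8.4.2 and both schedules (1.3.1, 1.3.2):** ask the existing 6.1.2.4 symptom list at the already planned day 1, 3 and 7 visits, covering the interval since the last contact, and record the answers as solicited AEs. Keep open-ended questioning for all other AEs.
- **9.4.5:** define solicited AEs as listed symptoms with onset from day 0 to day 7.
- **Where those visits have already taken place:** this version is dated October 13, 2022, and Appendix C describes the dose-escalation extension as ending on December 31, 2021, so a new checklist cannot help visits already held. For these, state in 9.4.5 which contacts used the list and limit solicited AEs to those contacts. Report symptoms obtained by open question separately.

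The cost is one CRF page, a few minutes at each of three existing visits, and more mild AEs recorded. No extra visits or blood draws are needed. The definition in 9.4.5 costs only text.
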